## **B.** Data Points

- Gut microbiota composition: fecal samples will be collected at Days 0, 28, 56 and the day when participants recover from COVID-19-like illness (if before Day 56)
- Clinical progress of COVID-19-like illness: 1) objective and subjective symptoms data will be collected twice a day from Day 1 to Day 28 or until they recover from COVID-19-like illness (whichever is later) and once a week thereafter until Day 56 (i.e. in the mornings of Days 35, 42, 49 and 56); and 2) COVID-19-like illness severity will be assessed at Days 1, 14, 28 and 56 using the categorization from FDA [18] and the Ordinal Scale for Clinical Improvement from the World Health Organization [19]
- Proportion of participants who are "alive and not admitted to the hospital" at Days 1, 14, 28 and 56
- Proportion of participants who visit the emergency room at Days 1, 14, 28 and 56
- Outcome of COVID-19-like illness (hospitalization or death) at Days 1, 14, 28 and 56
- Glucose homeostasis if the participant has T2DM: fasting blood glucose will be measured in the mornings from Day 1 to Day 28 or until they recover from COVID-19-like illness (whichever is later) and weekly thereafter until Day 56

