#### 4.7 Risks of Harm/Potential for Benefits to Subjects

#### A. Description of Risks of Harm to Subjects

# Reasonably Foreseeable Risks of Harm

Measuring fasting blood glucose during the study both involve a finger prick that pierces the skin. There may be a bruise, bleeding, or infection, at the place where the skin is pierced. However, infection is rare. Collecting fecal samples at home may impose inconvenience for the participants and their families. Participants may experience gastrointestinal symptoms (e.g. abdominal pain/discomfort, constipation, or bloating). These discomforts are minor and should not last longer than a few hours. Participants in the treatment group may experience hypoglycemia when they take NBT-NM108 if they are on diabetic medications. This product is low in digestible and simple carbohydrates and may reduce food intake. For participants who are already on diabetic medications (insulin and/or oral hypoglycemic agents) which lower blood glucose, the medication may reduce blood glucose beyond its normal level.

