# E. Minimizing Risks of Harm

Participants will be provided with oral and written instructions and supplies to collect fecal samples at home without direct physical contact with the specimens throughout the process. The specimens will be stored in a sealed container, a leak-proof secondary package (a sealable plastic bag lined with absorbent pads) and an outer package (e.g. a shipping box). Participants are not required to store the samples at home; they will mail the specimens to the research team using the shipping supplies provided.

To minimize adverse effects due to NBT-NM108, participants in the treatment group will be asked to gradually increase the dose to avoid adverse events associated with an acute increase in fiber intake. They will also be advised to drink enough fluids throughout the study including the amount of water taken together with NBT-NM108) to avoid constipation. Participants will be asked to monitor potential adverse events daily. If participants report an adverse event, a member of the study team will contact them to ask follow-up questions about the degree of severity (mild, moderate, or severe) and the frequency of the adverse events. The study physician (co-PI [name]) will assess the adverse events and, if necessary, she will instruct the participants to reduce the consumption of NBT-NM108 to a lower dose that has been tolerated, and so on. If the same level of discomfort continues i.e.. for three consecutive days, the treatment will be discontinued. Participants are also at asked to closely monitor their blood glucose level and discuss with their family physicians about adjusting their medications to prevent hypoglycemia.

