To monitor COVID-19-like symptoms, participants will evaluate their symptoms and report to the research team on Castor twice a day from Day 1 to Day 28 or until they recover from COVID-19-like illness (whichever is later) and once a week thereafter until Day 56 (i.e. the mornings of Days 35, 42, 49 and 56 as appropriate). For those who are hospitalized during the study, after they are discharged they will also be asked to evaluate their symptoms and report to the research team on Castor twice a day until they recover from COVID-19-like illness and once a week thereafter until Day 56. The study team will review the symptom diary within 24 h of each entry and follow up with the participants if the symptoms require medical attention. The study team will call all participants at least once a week to monitor their progress. Participants are also instructed to call 911 if they notice any of the following red flags: respiratory rate  $\geq$  30/min, pulse rate  $\geq$  125/min, oxygen saturation level  $\leq$  93%, severe shortness of breath at rest (inability to talk in full sentences), difficulty breathing, persistent pain/pressure in chest, cold/clammy/pale/mottled skin, new confusion or inability to wake up, blue lips or face, little or no urine output or hemoptysis. Participants with T2DM will be instructed to call the physician who normally manages their diabetes if their fasting blood glucose is < 60 mg/dL or > 300 mg/dL.

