To analyze the clinical data, Aalen's additive survival model will be used to test whether the impact of covarites on the cumulative hazard is time-dependent [35]. If the covariates do not vary with time, cox proportional hazards model will be subsequently used to adjust for age, gender, race/ethnicity, baseline COVID-19 severity, and whether the participant has taken treatments that may reduce COVID-19 severity (vaccination and monoclonal antibody treatment) as covariates. Survival analysis Kaplan-Meyer curves and log-rank test will be used to estimate and compare the risk of death and the risk of recovery, as a function of time, in participants with COVID-19-like symptoms [36, 37]. To compare the time to hospitalization, the time to recovery, the time to complete resolution of subjective symptoms, and the time to complete resolution of objective symptoms between treatment groups, we will use competing risks survival analysis (treating death or self-reported illness severity at Days 1, 14, 28 and 56 as a competing risk) [36, 38], use survival analysis without competing risk, and explore joint survival analysis and Bayesian survival model [39]. Specifically, cumulative incidence functions will be estimated and tested using Gray's test [40]. The Fine-and-Gray subdistribution hazard regression analysis [38] will be used to further adjust for age, gender, race/ethnicity, baseline COVID-19 severity, and whether the participant has taken treatments that may reduce COVID-19 severity (vaccination and monoclonal antibody treatment) as covariates. Proportion of participants who are "alive and not admitted to the hospital", proportions of participants who visit the emergency room at Days 1, 14, 28 and 56, have complete resolution of objective symptoms, have complete resolution of subjective symptoms and have complete resolution of subjective symptoms except cough and fatigue at Days 1, 14, 28 and 56 will be compared between groups using separate logistic regression analysis at each time point. Time for participants to have complete resolution of objective symptoms, complete resolution of subjective symptoms and complete resolution of subjective symptoms except cough and fatigue will be compared between groups using competing risks survival analysis described previously, treating death or self-reported illness severity at Days 1, 14, 28 and 56 as a competing risk [36, 38]. To compare the longitudinally (repeatedly) measured illness severity based on the Ordinal Scale for Clinical Improvement from the World Health Organization, body temperature (oral), oxygen saturation level, pulse rate, respiratory rate and fasting blood glucose between treatment groups, accounting for the effect of death, reported adverse event, or other appropirate competing risk, we will compare the treatment effect using the method of joint survival and longitudinal data analysis [41, 42], where each of the clinical outcomes (e.g., illness severity, body temperature (oral), and oxygen saturation level, etc.) will be modeled using linear mixed models, and death, reported adverse event, or other appropirate competing risk will be modelled using Weibull proportional hazards model [43]. Age, gender, race/ethnicity, baseline COVID-19 severity, and whether the participant has taken treatments that may reduce COVID-19 severity (vaccination and monoclonal antibody treatment) will be controlled as covariates in these statistical analyses, where appropriate. Within-group changes of main outcomes between groups will be modeled as change from pre- to post-treatment using ANOVA and modeled as the post-treatment value as the change itself with the pretreatment value entered as covariate using ANCOVA [44]. Lastly, alternative statistical methods will be explored to quantify the underlying differences between groups with respect to a time-to-event end point, robust methods include calculating ratio/difference of t-Year Survival Rates, ratio/difference of percentiles of survival functions, and ratio/differenceof restricted mean survival times or restricted mean time lost [45]. Statistical analyses described above will be conducted for both intent-to-treat dataset and per-protocal dataset. For each test of an outcome, we define the statistical significance by p<0.05. The false discovery rate [46] will be applied for multiple testing, where appropriate. Sensitivity analysis using multiple imputation methods [47] will be performed to handle the missing data. Other

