To analyze the clinical data, Aalen's additive survival model will be used to test whether the impact of covarites on the cumulative hazard is time-dependent [8]. If the covariates do not vary with time, cox proportional hazards model will be subsequently used to adjust for age, gender, race/ethnicity, baseline COVID-19 severity, and whether the participant has taken treatments that may reduce COVID-19 severity (vaccination and monoclonal antibody treatment) as covariates. Survival analysis Kaplan-Meyer curves and log-rank test will be used to estimate and compare the risk of death and the risk of recovery, as a function of time, in participants with COVID-19-like symptoms [9, 10]. To compare the time to hospitalization, the time to recovery, the time to complete resolution of subjective symptoms, and the time to complete resolution of objective symptoms between treatment groups, we will use competing risks survival analysis (treating death or self-reported illness severity at Days 1, 14, 28 and 56 as a competing risk) [10, 11], use survival analysis without competing risk, and explore joint survival analysis and Bayesian survival model [12]. Specifically, cumulative incidence functions will be estimated and tested using Gray's test [13]. The Fine-and-Gray subdistribution hazard regression analysis [11] will be used to further adjust for age, gender, race/ethnicity, baseline COVID-19 severity, and whether the participant has taken treatments that may reduce COVID-19 severity (vaccination and monoclonal antibody treatment) as covariates. Proportion of participants who are "alive and not admitted to the hospital", proportions of participants who visit the emergency room at Days 1, 14, 28 and 56, have complete resolution of objective symptoms, have complete resolution of subjective symptoms and have complete resolution of subjective symptoms except cough and fatigue at Days 1, 14, 28 and 56 will be compared between groups using separate logistic regression analysis at each time point. Time for participants to have complete resolution of objective symptoms, complete resolution of subjective symptoms and complete resolution of subjective symptoms except cough and fatigue will be compared between groups using competing risks survival analysis described previously, treating death or self-reported illness severity at Days 1, 14, 28 and 56 as a competing risk [9, 11]. To compare the longitudinally (repeatedly) measured illness severity based on the Ordinal Scale for Clinical Improvement from the World Health Organization, body temperature (oral), oxygen saturation level, pulse rate, respiratory rate and fasting blood glucose between treatment groups, accounting for the effect of death, reported adverse event, or other appropirate competing risk, we will compare the treatment effect using the method of joint survival and longitudinal data analysis [14, 15], where each of the clinical

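### Hypoglycemia is a named risk of NBT-NM108, but the plan compares glucose between arms only through means and schedules no by-arm count of low readings or hypoglycemia events

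*Protocol*

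**What the plan says.** **The risk.** Protocol section 1.1 A lists safety among the objectives. Section 4.7 A states that "Participants in the treatment group may experience hypoglycemia when they take NBT-NM108 if they are on diabetic medications" and explains that in such participants "the medication may reduce blood glucose beyond its normal level".

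**The data.** Protocol section 1.3 B, under "Glucose homeostasis if the participant has T2DM", says that "fasting blood glucose will be measured in the mornings from Day 1 to Day 28 or until they recover from COVID-19-like illness". The later of these two times applies, and readings then continue once a week to Day 56. Section 1.3 A has participants record adverse events and medication changes twice a day over the same period. Section 1.3 D lists fasting blood glucose as a secondary outcome at Days 1, 14, 28 and 56, with no threshold, event definition or favourable direction.

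**The low value.** Section 4.7 E tells participants with T2DM to call the physician who manages their diabetes "if their fasting blood glucose is < 60 mg/dL or > 300 mg/dL". The same section asks participants to "discuss with their family physicians about adjusting their medications to prevent hypoglycemia". Neither instruction is linked to an endpoint or an analysis.

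**The analysis.** Protocol section 6.1 compares "oxygen saturation level, pulse rate, respiratory rate and fasting blood glucose between treatment groups, accounting for the effect of death", a reported adverse event, or another competing risk. The glucose value goes into a linear mixed model and the competing event into a Weibull model. The Clinical Data Analysis part of the SAP repeats this ("respiratory rate and fasting blood glucose between treatment groups, accounting for the effect of death"). Both documents also plan ANOVA on change and ANCOVA for main outcomes, which are not defined.

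**Safety review.** Section 6.3 assesses safety from the course of the illness and from adverse event reports. The DSMB reviews these monthly and once 30% of the treatment group has completed 14 days.

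**The concern.** The harm described in section 4.7 lies in the lower tail of the glucose distribution, in people taking glucose-lowering drugs. A difference in means does not describe that tail. A few low readings among many ordinary ones barely move an arm mean, least of all when each arm has only a handful of participants with T2DM.

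The adverse event data do not fill the gap as planned. In section 6.1 and the SAP a reported adverse event is something the glucose model adjusts for, not a result tabulated by arm. Nothing in the documents makes a reading below 60 mg/dL an adverse event, so a low without symptoms may never be reported as one. The control is plain water, so participants know their arm and self-reports may be influenced by that. A meter reading is less exposed to it.

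At stake is whether a safety risk that the protocol itself names is reported by arm at all, when the data that bear on it are already collected.

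**Working it through.** No figure in the plan needs reproducing here. The check is textual first, then an illustration of how insensitive a mean is.

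**Step 1: which planned analyses touch glucose?**
- Joint model (Protocol 6.1, SAP): linear mixed model for the value, so a mean comparison.
- ANOVA or ANCOVA on main outcomes: also means, and it is not stated that glucose is a main outcome.
- Logistic and time-to-event analyses: listed for hospitalization, emergency visits, recovery, symptom resolution and death, not for glucose.
- Adverse events: competing risk only.

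None of them counts low readings or hypoglycemia events by arm.

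**Step 2: how many participants have T2DM?** Section 4.3 gives 100 in total and section 1.5 gives 1:1 allocation. Section 4.1/4.3 material on feasibility gives diabetes in 12% of confirmed cases at one testing centre; the T2DM share is not stated.
- If 12% applies to all 100: 100 × 0.12 / 2 = 6 per arm.
- If it applies only to the minimum of 40 confirmed cases in section 1.5: 40 × 0.12 / 2 = 2.4 per arm.

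**Step 3: how far do low readings move the mean?** The documents give no glucose means or SDs. Assumptions: 6 per arm, 28 daily readings, person mean 150 mg/dL, within-person SD 20, between-person SD 25 to 45. Replace three of the 28 readings by 55 mg/dL in each of k treated participants. The shift in the arm mean is k × 3 × (150 − 55) / (28 × 6) = 1.70k. The last column is the share of 20,000 simulated trials with p<0.05 in a two-sided t-test on person means, a simple stand-in for the treatment term of the mixed model.

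| Treated participants affected | Shift in arm mean (mg/dL) | Share with p<0.05 |
|---|---|---|
| 1 | −1.7 | about 5% |
| 2 | −3.4 | about 5% |
| 3 | −5.1 | about 5 to 6% |
| 6 (all) | −10.2 | about 7 to 10% |

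With half the treated arm affected, the test rejects about as often as it would by chance.

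**Step 4: what difference could the mean comparison detect?** For 80% power at two-sided 5%, by normal approximation: (1.96 + 0.84) × SD × √(2/6). This is 40 mg/dL for SD 25, 57 for SD 35 and 73 for SD 45.

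**Step 5: how different could the tail be?** Take total SDs, with within-person SD 20 and the rest between persons, and find the share of participants with at least one of 28 readings below 60.
- Mean 150, SD 35: about 5%.
- Mean 140, SD 40: about 14%.
- Mean 150, SD 45: about 12%, with no difference in means from the first case.

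These figures depend on the assumptions. Treating the 28 readings as independent draws from one common distribution would give 13%, 47% and 47%, which overstates the contrast because readings within a person are correlated. Part of the contrast also comes from assuming a larger SD in the treated arm. With the mean alone shifted (140, SD 35), the correlated figure is about 10%.

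**Step 6: what could a count show?** Against 0/6 in control, two-sided Fisher p is 0.45 for 2/6, 0.18 for 3/6, 0.06 for 4/6 and 0.015 for 5/6. If 0/6 is seen, the one-sided 95% upper limit is 1 − 0.05^(1/6) = 39%. The two-sided exact 95% interval runs to 1 − 0.025^(1/6) = 46%. A count makes the events visible; it does not give a powered test.

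**The case against.** The strongest reply is that the mixed model is not the safety analysis. Safety rests on adverse event reports, which participants record twice daily, the study physician assesses and the DSMB reviews monthly. A reading below 60 mg/dL prompts a call to the treating physician. Symptomatic hypoglycemia can therefore surface whatever the mean shows. The adverse event forms and the DSMB details are in appendices that are not available here, so hypoglycemia may be itemised there. This stands as a description of monitoring during the trial. It does not supply a planned by-arm result at the end.

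Two stronger readings are tempting and should not be drawn.
- A reader might infer that a lower treatment-arm mean would be reported as better glucose control. The documents do not say so. Section 1.3 B uses "Glucose homeostasis if the participant has T2DM" as a neutral label, and section 1.3 D states no direction. With detectable differences of 40 mg/dL or more, a significant lower mean is also unlikely.
- A reader might infer that medication reductions would conceal the harm. Section 4.7 E asks for that discussion in order to prevent hypoglycemia. A reduction that brings the mean back may have avoided lows rather than hidden them. It is still worth counting, because diabetic medication changes appear in no planned analysis.

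It is also fair that 60 mg/dL is an instruction to call a physician, not a definition of hypoglycemia, and that a morning fasting reading can miss lows later in the day, when most of the drinks are taken. A count of low fasting readings alone could therefore reassure falsely, so reported events must stand beside it. Section 4.7 A also ties the risk to participants on diabetic medication, so that group should be shown separately.

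**Conclusion.** The point holds as a gap in analysis and reporting, not in clinical monitoring. The protocol names hypoglycemia as a risk of the product, makes safety an objective and collects relevant data, but every planned between-arm glucose comparison is of means and adverse events enter only as a competing risk. As written, the trial can finish without a planned by-arm result on this harm.

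The size is modest. It concerns perhaps 6 participants per arm, or 2 to 3, and a secondary outcome in a 100-person feasibility trial. The insensitivity of the mean (shifts of 1.7 to 5.1 mg/dL, rejection near 5%) rests on assumed glucose values; the textual gap does not. The tail contrast of about 5% against 12 to 14% is illustrative only. The change is worth making because it is cheap and because a descriptive count matches the named harm better than a mean does.

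**What to change.** In Protocol section 6.1 and the Clinical Data Analysis part of the SAP, add one descriptive table by arm over Days 1 to 28. It covers participants with T2DM and is repeated for those on diabetic medication at baseline. It gives:

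1. the number and percentage with at least one fasting reading below 60 mg/dL, the value already in section 4.7 E, used here only as a reporting cut-off and not as a clinical rule;
2. low readings per reading taken;
3. the number with a reported hypoglycemia adverse event;
4. the number with a recorded reduction or stop of a diabetic medication.

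Give exact 95% confidence intervals for the participant proportions and make no significance claim. State under the table that morning fasting readings can miss lows at other times of day. Present any difference in mean glucose beside these counts.

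The cost is a few sentences in each document and one table, using glucose, adverse event and medication records already planned. No new measurement or change to participant management is involved. The intervals will be wide, and the table should say so.

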#### 6.2 Data Security

The study data will include two key components: 1) a master code identifier that contains the personal information of the participants and the participant code assigned to them; and 2) study data files that contain all the de-identified data generated in this trial. Participants' hard copy files will be kept in locked cabinets only accessible by authorized research personnel in a secured building. Electronic data will be stored on Castor, a cloud-based clinical data management platform certified for ISO 27001 (Standards for Information Security Assurance). The data will only be accessible to authorized research personnel, who will have individual accounts that require strong passwords. The master code identifier and the data files will be kept in two separate locations. The master code identifier is only accessible to the Principal Investigator and research personnel who schedule appointments and shipments. Data in hard copies and the master code identifier will be kept for 6 years after study completion, then any hard copies will be shredded and the master code identifier will be permanently deleted from the server. As study data will then exist in de-identified form, the electronic data files will be kept indefinitely.

